A multidisciplinary EM implementation team developed a LOF assessment tool targeted for the CICU patient population. The assessment tool was created to be easy to use, quantitative, nurse-driven, and potentially generalizable to other CICUs. The creation of the EM team and EM program was an initiative of the Quality of Care Committee in the Division of Cardiology at the Jewish General Hospital.

All patients admitted to the CICU are eligible for the EM program, except for patients meeting pre-defined hemodynamic, respiratory, neurologic, or in-dwelling device criteria. The exclusion criteria were chosen based on expert guidelines for EM safety³¹ and adapted for the acute cardiovascular patient population through collaboration with the multidisciplinary EM team.

For entry into our study, the inclusion criterion is age ≥ 60 years and exclusion criteria are CICU stays less than 24 hours and patients with prehospital LOF 0 (immobile), LOF 1 (bedbound) or 2 (can sit in chair only). Cardiac surgery patients will also be excluded. Patients with a pacemaker or defibrillator will not be included in the bioimpedance substudy (contraindication for use of bioimpedance scale). For the pre-intervention cohort, patients will be prospectively enrolled over a 3-month period by a member of the research team during CICU admission. Following the 3-month pre-intervention period, the intervention (EM program) will be implemented and patients will be prospectively enrolled during CICU admission over a 12-month period by a member of the research team. Informed consent will be obtained for all participants during enrolment by a member of the research team.

Pre-intervention

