housed in the Frailty Assessment Unit of the JGH's cardiovascular ward and can be used at the point of care. The BIA scales provide a full analysis of body composition in less than 1 minute, including determination of skeletal muscle mass. There are no risks associated with the bioimpedance scale, except for patients with a permanent pacemaker or defibrillator, who will be excluded from this trial (the reason being that bioimpedance scale currents may disrupt the functioning of pacemakers or defibrillators).

Post-discharge follow-up

One month and 12-months post-discharge a member of the research team will call participants by phone to assess for health-related quality of life and functional status. The member of the research team will determine the current LOF and administer the Short-Form 36-Item Health Survey (SF-36) and Barthel index.

Outcome Measures

The primary outcome will be the LOF at CICU discharge and at 1 and 12 months post-hospitalization. Secondary outcomes are (1) Short Form (SF)-36 physical component summary score at 1 and 12 months, (2) SF-36 mental component summary score at 1 and 12 months, (3) Barthel index score at 1 and 12 months, (4) length of hospital stay, and (5) discharge to healthcare facility (including rehabilitation facility, convalescence, transfer to another acute care facility, and long-term care placement).

The SF-36 is a patient-reported survey of health and is the most widely used health-related quality of life instrument.⁵³ The physical and mental component scores are subsets of the SF-36 with score ranges from 0-100 and are calibrated for an average score of 50, using Canadian normative data, with higher scores indicating less disability.⁵⁴ The Barthel index is a disability measure validated in elderly cardiac patients that incorporates ten activities of daily living (i.e., feeding, dressing, incontinence).^{55, 56} Only two components of the Barthel index address mobility issues (transfer and mobility), so there is minimal direct overlap with the LOF scale score. The score range is 0–20, with lower scores indicating increased disability.

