In the patients wearing the accelerometer, data will be recorded on the total time spent in each mobility position, the daily average time spent in each mobility position, the average duration of time for each bout of sitting, standing, and walking, and sleep duration. The step count will also be recorded. The change in skeletal muscle mass from CICU admission to hospital discharge will be recorded.

We will determine which covariates predict improvement in LOF (“responsiveness”) and which ones do not (“non-responsiveness”). We will assess the recovery of physical function at 1 month and 12 months as measured by the SF-36 physical component summary score. We will compare the SF-36 scores of the highest scoring tertile of LOF on hospital discharge with the lowest scoring tertile. We will also compare hospital readmission at 30 days and discharge home vs. healthcare facility.

For safety, we will record the composite and individual components of the number of falls, injuries, and dislodgements over the total number of attempted mobility activities. The results from the intervention cohort will be compared to the pre-intervention cohort for all results.

Data Collection Procedures

Following discharge, a member of the research team will capture the following hospitalization data from the electronic medical record (Chartmaxx, Quest Diagnostics, Madison, New Jersey) for each subject: age, sex, primary admission diagnosis, comorbidities, level of function assessments, CFS score, length of CICU stay, length of hospital stay, discharge location, and referral to cardiac rehabilitation.

Availability of Participants

In the fiscal year 2016-2017, there were 1,356 admissions to the JGH CICU (mean age 68 years old; 477 female (35%)). There were 1,034 patients (76.3%) age ≥ 60 years old. The mean CICU length of stay was 3.3 days and the mean hospital length of stay was 9.5 days. Only one in five patient stays was less than 24 hours in length.

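### Secondary outcome 5 counts a return to the referring hospital, and on its general wording to an existing care home, as discharge to a healthcare facility, and the patient's origin is not recorded

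*Combined protocol and SAP*

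**What the plan says.** All references are to the combined protocol and SAP, section VI (Methods), unless stated.

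- **Outcome.** Outcome Measures lists, as the fifth secondary outcome, "discharge to healthcare facility (including rehabilitation facility, convalescence, transfer to another acute care facility, and long-term care placement"). The same subsection later adds a two-way comparison, "discharge home vs. healthcare facility". Neither has a category for return to the previous residence or to the referring hospital.
- **Entry.** Design, participants and setting states that "the inclusion criterion is age ≥ 60 years and exclusion criteria are CICU stays less than 24 hours". It also excludes "prehospital LOF 0 (immobile), LOF 1 (bedbound) or 2 (can sit in chair only") and adds "Cardiac surgery patients will also be excluded". For the mobilization program itself, "All patients admitted to the CICU are eligible for the EM program, except for patients meeting pre-defined hemodynamic, respiratory, neurologic, or in-dwelling device criteria". Residence before admission and source of admission are not among these criteria.
- **Data.** The list in Data Collection Procedures ends with "length of CICU stay, length of hospital stay, discharge location, and referral to cardiac rehabilitation". The list under Pre-intervention also includes the discharge destination. Neither list has a field for where the patient lived or was admitted from.

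**The concern.** Section IV.B describes the purpose of early mobilization relative to the patient's state before hospital: keep or restore earlier function. LOF follows that logic, because a prehospital value is recorded. Discharge destination does not, because it has no baseline.

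Two kinds of eligible patient can therefore register an event that says little about mobility. One is a long-term care resident who can stand or walk and goes back to the same residence at full prehospital function. The other is a patient sent to this tertiary unit by another hospital and then sent back.

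Events of this kind, equally common in both cohorts, pull the comparison toward no difference. If they become more or less common between the 3-month pre-intervention period and the 12-month intervention period, they can create or hide a difference. The cohorts are not randomised. The covariates named under Data Analysis belong to the LOF model and include neither residence nor admission source.

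**Working it through.** **1. Reading the text.** The documents give no expected rate, effect size or power for this outcome, so there is no figure to reproduce.

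| Patient | Eligible? | Scored as an event on return to origin? |
|---|---|---|
| Transferred in from another hospital | Yes; no criterion on source | Yes; transfer to another acute facility is named in the definition |
| Long-term care resident, prehospital LOF 3–5 | Yes; only LOF 0–2 is excluded | Yes under the general heading and the home/facility split; less clear under the word 'placement' |
| Long-term care resident, prehospital LOF 0–2 | No | Not applicable |

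**2. Equal share in both cohorts.** Let *f* be the combined share of such patients, all assumed to return to origin, and *p* the true rate of new facility discharge in everyone else. The observed rate is *f* + (1 − *f*)*p*, so the risk difference is multiplied by (1 − *f*). Assumed true rates are 20% before and 14% after: difference 6.0 points, risk ratio 0.70.

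| *f* (assumed) | Before | After | Difference | Risk ratio |
|---|---|---|---|---|
| 5% | 0.05 + 0.95 × 0.20 = 24.0% | 0.05 + 0.95 × 0.14 = 18.3% | 5.7 points | 0.76 |
| 10% | 0.10 + 0.90 × 0.20 = 28.0% | 0.10 + 0.90 × 0.14 = 22.6% | 5.4 points | 0.81 |
| 15% | 0.15 + 0.85 × 0.20 = 32.0% | 0.15 + 0.85 × 0.14 = 26.9% | 5.1 points | 0.84 |

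Full return is the worst case. If only a fraction *r* go back and the rest behave like other patients, *f* is replaced by *f* × *r*. With *f* = 10% and half returning, the 5% row applies.

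**3. Unequal share.** Raising the share by 5 points in the pre-intervention cohort alone adds 0.05 × (1 − 0.20) = 4.0 points to the difference. Raising it in the intervention cohort alone removes 0.05 × (1 − 0.14) = 4.3 points. With no true effect, the spurious difference is 0.05 × (1 − *p*): 4.5, 4.0 and 3.5 points for *p* = 10%, 20% and 30%.

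**4. Size against precision.** Availability of Participants expects about 75 and 300 patients. For 20% vs 14%, the 95% half-width is 1.96 × √(0.20 × 0.80/75 + 0.14 × 0.86/300) = 1.96 × 0.0503, or 9.9 points. The dilution in step 2 is 0.3 to 0.9 points.

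**5. Cost of a smaller denominator.** This uses a second assumed pair, 20% vs 10%, with 75 vs 300 patients, two-sided alpha 0.05 (also assumed) and a normal-approximation test with pooled variance under the null. Power is 0.64 at *f* = 0. At *f* = 10% the rates become 28% vs 19% and power is 0.41. Restricting to the 90% not admitted from a facility (67.5 vs 270) gives 0.60.

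**The case against.** The strongest reply has five parts.

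- **Placement.** The word ordinarily suggests a new move into care, so an existing resident's return need not qualify. This stands as an ambiguity. It does not settle the matter: a care home still falls on the facility side of the home/facility comparison. It also does not touch the referring-hospital case, which the definition names.
- **Numbers.** No section says how many patients come from care homes or other hospitals. The pilot figures in section V point to mobile, locally followed patients: among the 16 who were eligible, mean prehospital LOF was 4.7 (SD 0.6), and 12 (75%) were already followed by a hospital-affiliated cardiologist. This stands; the share may be small. A reader might infer from the tertiary setting that repatriation is common, but the documents do not show it.
- **Repairability.** A reader might infer that the outcome could never be corrected afterwards. That goes too far. Discharge location is already extracted, so acute transfers could be set apart, and origin could be sought by returning to the charts. What stands is narrower: the listed data cannot tell a return from a new placement or transfer.
- **Imbalance.** A reader might take a 5-point chance imbalance as nearly equal to the assumed 6-point effect. By step 3 it is worth 4.0 to 4.3 points, about 67% to 72% of it. A chance imbalance is also ordinary sampling variation, already within the standard error; only a systematic change in case mix would bias the result, and the documents show no mechanism for one.
- **Acute transfers.** It is tempting to stop counting every acute transfer as an event. That would misclassify patients admitted from the community and transferred elsewhere because they worsened.

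**Conclusion.** The point holds in limited form. As written, the rule scores return to a referring hospital as an event and, on its general wording, also return to an existing care home; the planned data cannot identify either. The documents do not use the term adverse for this outcome. That it is unfavourable follows from its use as an effectiveness measure set against going home.

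Under the assumptions shown (true rates 20% vs 14%, everyone returning, combined share 5% to 15%), the loss is 0.3 to 0.9 points of risk difference, and the risk ratio moves from 0.70 to between 0.76 and 0.84. The absolute dilution is small beside a half-width of about 10 points. A systematic 5-point change in share between cohorts would matter more, at 4.0 to 4.3 points, but nothing in the documents shows that one will occur.

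This is one of five secondary outcomes, and the primary LOF outcome is not affected. Low priority: a cheap improvement.

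**What to change.** 1. Add two fields to the chart extraction in both cohorts: residence before admission (home or facility) and source of admission (community or another hospital).
2. Define secondary outcome 5 as new discharge to a healthcare facility among participants living at home before admission.
3. Make return to the referring hospital its own category, reported separately by cohort, and state in advance how it enters the denominator. A new transfer to another acute facility of a patient admitted from the community remains an event.
4. Use the same definition for the home versus facility comparison, and report the all-facility definition now in the protocol as a sensitivity analysis.

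The cost is two items from a record already being reviewed and a slightly smaller denominator for this one outcome. Care-home residents stay in the LOF comparison. Eligibility, the intervention and the primary analysis do not change.

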Early Mobilization of Older Adults in the Cardiovascular Intensive Care Unit

I. RESEARCH QUESTION

Is an early progressive mobilization program safe, feasible, and effective in older adults in the Cardiovascular Intensive Care Unit (CICU)?

II. HYPOTHESES

1. An early mobilization (EM) program is safe, feasible, and effective in older adults in a Canadian tertiary care academic CICU.
2. Level of function on CICU discharge and time spent lying in bed during hospitalization is associated with health-related quality of life scores and functional status at longer-term follow-up.

III. SPECIFIC AIMS

Aim #1: To determine functional status and longer-term patient-centered outcomes of older adults admitted to the CICU prior to the implementation of the EM program (“pre-intervention” cohort)

Aim #2: To assess the safety and feasibility of an EM program in a Canadian academic tertiary care CICU

Aim #3: To determine the effectiveness of EM at improving the functional status of older adults during CICU admission and improving longer term patient-centered outcomes (“intervention” cohort)

Aim #4: To evaluate the association of daily time spent lying in bed with functional status at CICU discharge and following hospital discharge

Aim #5: To assess the amount of skeletal muscle mass loss during admission for acute cardiovascular disease

IV. BACKGROUND

A. Physical Function and Impairment in Older Adults in the Critical Care Unit

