To introduce the EM protocol to the nursing staff, the nurse and physician champion will provide a series of in-service training sessions. Physicians routinely caring for older adults in the CICU and rotating trainees will receive education in the CICU through “Lunch and Learn” conferences. Weekly audits will be performed by the nurse champion to assess for adherence to the EM protocol. Reminders and further education will be provided if necessary. Monthly status reports will be created and disseminated to the nurses and the CICU team.

Frailty will be assessed on admission using the Clinical Frailty Scale (CFS) by the patient’s nurse or a member of the research team (Appendix B).³² The CFS is a simple bedside assessment tool that uses a single global judgement-based measure to assign a score from 1 (very fit) to 9 (terminally ill) with increasing scores from 5 to 8 indicating more advanced frailty.²⁰ The CFS correlates with more comprehensive frailty tools, has been shown to accurately diagnose frailty in critically ill and acute cardiac populations, and provides short and long-term prognostic information.^{20, 21, 33}

Enrolled participants will be approached to participate in this prospective substudy. Patients accepting participation will be asked to wear an accelerometer monitor during CICU stay until the end of hospitalization to capture the time spent in each mobility position. Body composition parameters including skeletal muscle mass and fat mass will be measured daily with a segmental multi-frequency bioimpedance scale.

Instruments

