From the pilot data, we conservatively estimate that about one-third of patients will not be eligible for the study and about 70% will agree to participate. We estimate that the loss of patients to 12 month follow-up will be approximately 10% as the vast majority of CICU patients are followed by hospital-affiliated cardiologists prior to admission or are assigned to one following CICU discharge. Given these estimates, approximately 75 patients are expected to be enrolled and followed during the pre-intervention period and 300 patients are expected to be enrolled and followed during the 12 month intervention period.

Data Analysis

Since the response variable, LOF mobility, is an ordinal variable measured at different timepoints, a cumulative logit model for repeated measurements will be fitted using generalized estimating equations. The model permits us to take into consideration the structure of the correlation between the observations. The model will then be adjusted using covariates of interest, such as age, sex, EM adherence, time spent lying in bed, and illness severity score. Predictors of change in LOF during CICU stay and following hospitalization will be assessed using linear regression. Predictors of EM adherence will also be evaluated using linear regression. All statistical analyses will be performed using SAS version 9.4 by [name], a senior biostatistician affiliated with the Lady Davis Institute Center for Epidemiology.

VII. RESOURCE AVAILABILITY AND SUPPORT

The CICU at the JGH has 16 beds equipped for advanced hemodynamic support and 32 ward beds with telemetry available. Patients are admitted to the CICU mainly for acute primary cardiovascular disease.

The nurse champion's role is to attend EM team meetings, provide education to nursing and clinical partners, and ensure nursing adherence to the protocol. A review of the CICU environment conducted with physiotherapists from the EM team has ensured that the CICU is already equipped with the standard equipment necessary for patient mobilization, particularly for bedbound and immobile patients, and nurses have been trained to use the equipment.

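### No exposure window is set for lying time in Aim 4; if the full wear period is used, about 65% of mean hospital days fall after the CICU-discharge LOF being explained

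*Combined protocol and SAP*

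**What the plan says.** All references are to the combined protocol and SAP.

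- **Aim** (III. Specific Aims, Aim 4): "To evaluate the association of daily time spent lying in bed with functional status at CICU discharge and following hospital discharge". One exposure serves an in-hospital outcome and later outcomes.
- **Hypothesis** (II. Hypotheses, no. 2): "time spent lying in bed during hospitalization is associated with health-related quality of life scores and functional status at longer-term follow-up". This is the only place that names an exposure period, and it does so for the later outcomes only.
- **Wear period** (VI. Methods, Intervention): substudy patients are asked to "wear an accelerometer monitor during CICU stay until the end of hospitalization". No other period is described.
- **Recorded variables** (VI. Methods, Outcome Measures): "data will be recorded on the total time spent in each mobility position, the daily average time spent in each mobility position". There is no separate value for the CICU.
- **Outcome times** (VI. Methods, Outcome Measures): "The primary outcome will be the LOF at CICU discharge and at 1 and 12 months post-hospitalization".
- **Model** (VI. Methods, Data Analysis): a cumulative logit model for repeated LOF measurements, fitted by generalized estimating equations (GEE) and adjusted for covariates "such as age, sex, EM adherence, time spent lying in bed, and illness severity score". Lying time appears once, without a period. Predictors of LOF change during the CICU stay and afterwards are to be examined by linear regression.

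**The concern.** An exposure offered as a predictor should be complete before the outcome is measured. A whole-stay summary meets that condition for LOF at 1 and 12 months. It does not meet it for LOF at CICU discharge, because it includes ward days that come later. No single lying-time value suits all three outcome times.

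The direction of the possible error matters. A patient who leaves the CICU with low LOF may well lie more on the ward. A summary that includes the ward could then be associated with CICU-discharge LOF even if lying time in the CICU had no bearing on it. The same applies to any regression of LOF change during the CICU stay on lying time: ward data cannot predict a change that is already complete. Section IV.D, item 6 presents lying time as something care might reduce, so a reversed association could be taken as support for an intervention.

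**Working it through.** The plan states no share of monitored time before or after CICU discharge, so there is no figure of its own to reproduce.

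**Inputs.** VI. Methods, Availability of Participants: "The mean CICU length of stay was 3.3 days and the mean hospital length of stay was 9.5 days". These are means over all 2016-2017 CICU admissions. The same paragraph says that about one stay in five was under 24 hours, and CICU stays under 24 hours are excluded from the study.

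**Step 1: share of days after CICU discharge.**
(9.5 - 3.3)/9.5 = 6.2/9.5 = 65.3%. The share before is 3.3/9.5 = 34.7%.

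**Step 2: sensitivity of that share (all assumptions mine).**
- *Short stays removed.* Take the 20% as CICU stays averaging x = 0 to 1 day. The eligible CICU mean is (3.3 - 0.2x)/0.8 = 4.1 to 3.9 days. With the hospital mean held at 9.5, the share is 57-59%. If instead the short-stay patients' ward stay is set at 0 to 6.2 days, the share is 60-67%.
- *Hospital days before the CICU.* One day: 5.2/8.5 = 61%. Two days: 4.2/7.5 = 56%.
- *Wear starting late.* A delay of 0.5 day: 6.2/9.0 = 69%. A delay of 1.5 days: 6.2/8.0 = 78%.

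The range is 56-78% of days.

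**Step 3: total lying hours instead of days.** For a daily average, each monitored day counts equally and Step 2 applies. For total lying time, the share depends on hours per day. With a CICU and b ward hours lying, it is 6.2b/(3.3a + 6.2b). Assumed pairs (a, b) of 22/16, 20/14 and 20/10 give 58%, 57% and 48%.

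**Step 4: illustrative spurious correlation.** Suppose CICU lying time is unrelated to CICU-discharge LOF, ward lying time correlates r with it, the two lying times have equal SDs, and they correlate c with each other. The whole-stay average then correlates with LOF at

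0.653r / sqrt(0.347² + 0.653² + 2c × 0.347 × 0.653).

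| c | Multiplier of r | r = -0.3 | r = -0.5 |
|---|---|---|---|
| 0 | 0.653/0.739 = 0.88 | -0.26 | -0.44 |
| 0.5 | 0.653/0.879 = 0.74 | -0.22 | -0.37 |

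The values of r and c are assumptions; the documents give neither.

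**The case against.** A reader might infer that the plan has chosen a whole-stay exposure for the CICU-discharge outcome. The documents do not support that. The wear period is stated, but neither the summaries nor the covariate carries a window, and the one explicit reference to the whole hospitalization is tied to longer-term outcomes, where it is properly ordered. An analyst could derive a CICU-only value from continuous monitoring. This objection stands: the defect is an undefined window, not a stated wrong one. But nothing in the plan requires the CICU-only value, and the only period described leads to the full-wear summary by default.

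A reader might also infer that two-thirds of the exposure of substudy patients follows the outcome. The 65% is a ratio of mean stays over admissions of all ages, including stays the study excludes. It counts hospital days rather than lying hours. It indicates size and is not an estimate for the substudy.

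Third, the correlations in Step 4 largely return what is put in: with independent CICU and ward lying time, the answer is 0.88 times the assumed r. Independence within a patient is doubtful, hence the second row. They are also unadjusted correlations, whereas the planned model adjusts for age, sex and illness severity. Shared severity could produce a link without reverse causation. So the whole-stay value could show a spurious association; the documents do not show that it would.

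Finally, the scope is narrow. Lying time exists only in an optional substudy with five monitors, and one of the three LOF times is affected.

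**Conclusion.** The point holds as a conditional one. The plan sets no lying-time window that ends before the CICU-discharge LOF, and it enters a single undated covariate in a model whose first outcome is that LOF. If the full-wear summary is used, about 65% of mean hospital days (56-78% across the assumptions tried) follow that outcome, and reverse causation becomes possible. Any spurious correlation is illustrative only: -0.26 to -0.44, or about -0.22 to -0.37 if CICU and ward lying time correlate 0.5.

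This is more than a missing detail, because no single window is right for every outcome in the model. It reaches only the accelerometer substudy and the CICU-discharge timepoint, including any analysis of LOF change during the CICU stay. It would be wrong to read it as undermining the 1- and 12-month half of Aim 4, where a whole-stay exposure precedes the outcome.

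**What to change.** State two exposures in Outcome Measures and Data Analysis:

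1. **For CICU-discharge LOF and change in LOF during the CICU stay:** mean daily lying time from start of wear to CICU discharge. LOF is recorded on the day of transfer, and the documents list no assessment time. If no time is available, cut at the CICU transfer date and say whether the transfer day counts.
2. **For the 1- and 12-month outcomes only:** mean daily lying time over the whole stay.

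Also state how these enter the model. One option is a time-varying covariate with a covariate-by-timepoint interaction, so that each outcome time has its own coefficient, under an independence working correlation. That working structure matters because the later exposure value may depend on the earlier outcome, and other working correlations can then bias the GEE estimates. The simpler option is a separate model for the CICU-discharge outcome.

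**Cost:** a few sentences and a date cut in the data step. Monitoring is continuous and length of CICU stay is already collected, so no new patient measurement should be needed. The downside is precision: the CICU-only average rests on about 3.3 monitored days on average instead of 9.5, and fewer if wear starts late.

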Prior to the implementation of the EM intervention, nurses will ascertain and record the prehospital LOF, admission LOF, and LOF on the day of CICU transfer (Appendix A), but will continue usual mobilization practices. Patients who meet eligibility criteria for the EM intervention will be prospectively enrolled over a 3-month period (“pre-intervention cohort”) by a member of the research team during CICU admission. Informed consent will be obtained by a member of the research team. Following discharge, a member of the research team will review the medical record to extract demographic data (age, sex), comorbid illnesses, primary admission diagnosis, frailty status, adverse events during mobilization (falls, dislodgements, and injuries), mobilization activities, length of critical care unit stay, length of hospital stay, mortality, and discharge location.

Intervention

On admission to the CICU, the patient’s treating nurse will assess the patient for the EM program. Patients participating in the EM program will be assessed for enrolment in our study by a member of the research team and will obtain informed consent during CICU admission (“intervention cohort”). The potential participants are likely to be competent and medically fit to be approached for informed consent as patients who are not medically fit will be excluded from the early mobilization program based on clinical factors, which include hemodynamic criteria.

The EM program consists of a progression of functional activities from LOF 0 (lowest mobility) to 5 (highest mobility). Each LOF has 3 primary activities designed to promote the patient to the next level. The nurse will begin with mobility activities based on the LOF that matches the patient’s current status. The nurse and clinical partner will attempt and/or complete each LOF activity once per shift. Physiotherapy assistance is available if required, although not obligatory. Nurses will also provide documentation and education to patients and families on

how to perform and assist with certain activities. LOF, activity attempts/completion, and adverse safety events will be recorded on an EM flowsheet. The intervention will start while the patient is in the CICU and will continue until discharge from the CICU.

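### The only planned analysis linking in-hospital LOF to SF-36 uses tertiles of LOF at hospital discharge, whereas Hypothesis 2 names LOF at CICU discharge; the tertiles have no cut points

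*Combined protocol and SAP*

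**What the plan says.** All references are to the combined protocol and SAP.

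- **Section II, Hypothesis 2:** "Level of function on CICU discharge and time spent lying in bed during hospitalization is associated with health-related quality of life scores", and also with functional status at longer-term follow-up.
- **Section VI, Outcome Measures, primary outcome:** "The primary outcome will be the LOF at CICU discharge and at 1 and 12 months post-hospitalization".
- **Section VI, Outcome Measures, the analysis at issue:** "We will compare the SF-36 scores of the highest scoring tertile of LOF on hospital discharge with the lowest scoring tertile". The sentence before it concerns the SF-36 physical component score at 1 and 12 months. The same part adds: "The results from the intervention cohort will be compared to the pre-intervention cohort for all results".
- **Section VI, Pre-intervention:** "nurses will ascertain and record the prehospital LOF, admission LOF, and LOF on the day of CICU transfer".
- **Section VI, Intervention:** "LOF, activity attempts/completion, and adverse safety events will be recorded on an EM flowsheet". Also: "The intervention will start while the patient is in the CICU and will continue until discharge from the CICU". The scale runs from 0 to 5.
- **Section VI, Data Collection Procedures:** the items extracted include "level of function assessments, CFS score, length of CICU stay, length of hospital stay, discharge location", with no time points attached to the LOF assessments.
- **Section VI, Data Analysis:** the response is LOF, change in LOF or EM adherence. No model has SF-36 as the response.

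**The concern.** The tertile sentence is the only place where the plan says how the link between LOF and quality of life in Hypothesis 2 will be examined. If its exposure is not the one hypothesised, the hypothesis has no matching analysis, and a result at one time point could be reported as if it answered the question about the other.

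The grouping is a separate problem. Tertiles of a six-level score depend on where ties fall, and the plan states no cut points, no tie rule, and no choice between pooled and within-cohort tertiles. The groups would then be settled after the data are seen. Comparing only the extremes also discards the information in the middle group.

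**Working it through.** The plan gives no figure for this analysis (no group sizes, cut points, effect size or power), so there is nothing to reproduce.

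**1. Time points side by side**

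| Place | In-hospital LOF time point |
|---|---|
| Hypothesis 2 | CICU discharge |
| Primary outcome | CICU discharge |
| Pre-intervention recording | prehospital, admission, day of CICU transfer |
| Intervention recording | EM flowsheet, for a program that ends at CICU discharge |
| Extraction list | LOF assessments, times not given |
| SF-36 tertile analysis | hospital discharge |

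Only the tertile sentence uses hospital discharge. The two time points coincide for a patient who goes home directly from the CICU, but not for one transferred to a ward.

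**2. Could the scores pile up at the top?**

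Section V gives a prehospital LOF of mean 4.7, SD 0.6, in the pilot's eligible patients: 26 − 10 = 16. Enumerating every allocation of 16 whole-number scores on 0–5 that fits these values to rounding leaves two:

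- 12, 3 and 1 patients at LOF 5, 4 and 3: mean 75/16 = 4.69, SD 0.60 (divisor n − 1); 12/16 = 75% at LOF 5.
- 13, 2 and 1 patients: mean 76/16 = 4.75, SD 0.58; 13/16 = 81% at LOF 5.

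A ceiling is therefore possible on this scale, but these are prehospital scores. LOF at hospital discharge is not given.

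**3. What tertiles would look like**

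The means and SDs below are assumptions. The low end adds the CICU-stay gain reported from another site on a 1–5 scale to the pilot admission mean: 2.3 + 0.53 to 0.70 = 2.83 to 3.00. The high end is the pilot prehospital value. The rows between fill the gap. Each row uses the maximum-entropy distribution on 0–5 with that mean and SD. Two tie rules are shown: cuts nearest to equal thirds, and cuts at the levels where the cumulative share first reaches 1/3 and 2/3.

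| Mean, SD | % at LOF 0/1/2/3/4/5 | Nearest thirds, low/mid/high % | Quantile rule, low/mid/high % |
|---|---|---|---|
| 2.8, 1.2 | 2.8/11.4/25.6/31.4/21.1/7.7 | 40/31/29 | 40/31/29 |
| 3.0, 1.2 | 2.0/8.9/22.3/31.3/24.6/10.8 | 33/31/35 | 65/25/11 |
| 3.5, 1.2 | 1.2/5.0/14.1/25.7/30.5/23.5 | 46/31/24 | 46/31/24 |
| 4.0, 1.0 | 0.2/1.4/6.7/19.4/34.5/37.8 | 28/34/38 | 62/38/none |
| 4.5, 0.8 | 0.1/0.6/2.3/8.0/24.3/64.8 | 11/24/65 | 35/65/none |
| 4.7, 0.6 | 0.0/0.1/0.8/4.1/18.8/76.2 | 5/19/76 | one group only |

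At mean 3.0 the highest tertile is 35% or 11% of patients, depending only on the unstated rule, because the share at LOF 2 or below falls just under one third.

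**4. Cost of setting the middle aside**

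Assume SF-36 is linear in LOF with constant residual variance. The efficiency of the extreme-group contrast relative to the trend test is then

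E = (m_H − m_L)² × p_H p_L / (p_H + p_L) / Var(LOF),

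where p is the share and m the mean LOF in the high (H) and low (L) groups. With the nearest-thirds cuts:

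- Mean 3.0: (4.305 − 1.611)² × (0.354 × 0.332 / 0.686) / 1.44 ≈ 0.86.
- Mean 3.5: (5 − 2.398)² × (0.235 × 0.460 / 0.695) / 1.44 ≈ 0.73.
- Mean 4.0, SD 1.0: (5 − 2.635)² × (0.378 × 0.277 / 0.655) / 1.00 ≈ 0.89.

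So the contrast keeps roughly 73% to 89% of the trend test's efficiency in these cases.

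**The case against.** The strongest reply is that the wording is a slip, that comparing extremes is an ordinary descriptive choice, and that Hypothesis 2 claims only an association, which an unadjusted contrast can address. Much of this stands. It may be a slip, but then the text needs correcting. The absence of adjustment is not in itself an error against the hypothesis; adjusting for prehospital LOF makes the result more informative.

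A reader might infer four stronger points that the documents do not support:

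- **LOF at hospital discharge will not be collected.** The LOF form and EM flowsheet are not shown and the extraction list is open-ended. The most that can be said is that no available text names such an assessment.
- **The exposure is measured about 6 days late.** The difference 9.5 − 3.3 = 6.2 days subtracts two mean stays over all 2016–2017 CICU admissions, including patients under 60 and stays under 24 hours. It is not a measured interval from CICU to hospital discharge in the study population.
- **The tertiles will collapse.** That needs discharge LOF to resemble prehospital LOF. Section IV.A cites up to 70% of older critical care patients not regaining prehospital activity by discharge, which points the other way, although it is an upper figure from general critical care. With cuts nearest to thirds, three usable groups persist up to a mean of about 4.0.
- **A third of the patients, 125 of the expected 375, are lost.** That figure assumes equal thirds, which ties do not guarantee.

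**Conclusion.** The mismatch is established from the text alone: the one analysis serving the quality-of-life part of Hypothesis 2 for LOF uses a different exposure from the hypothesis and the primary outcome, at a time point that the available recording schedule does not name.

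The grouping is under-specified. How much that matters depends on a distribution the documents do not give: under the assumptions shown, the split runs from near-thirds to no separate top third. The efficiency loss from dropping the middle group is moderate and rests on an assumed linear relation.

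This should be corrected, but it concerns a secondary analysis. The primary outcome and the expected enrolment are untouched.

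**What to change.** Replace the tertile sentence with something like this: *SF-36 physical and mental component scores at 1 and 12 months will be regressed on LOF at CICU discharge, entered as ordered levels with a trend test, in all patients with SF-36 data, adjusted for prehospital LOF, CFS score, age, sex and cohort. The physical score at 12 months is the main test; the others are supportive. Mean scores and numbers of patients will be shown by LOF level.*

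All these variables are already planned. Prehospital LOF is also needed to apply the entry criteria. The illness severity score is named as a covariate in Data Analysis but is missing from the extraction lists, so it is optional here and should be added only if it is extracted.

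If hospital discharge is truly intended, reconcile it with Hypothesis 2, name that assessment in the recording schedule for both cohorts, fix the LOF cut points in advance, and say whether groups are pooled across cohorts. That may cost one further LOF assessment per patient.

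The downside of the regression is that the trend test assumes a monotone relation; the means by level will show whether that is reasonable.
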